14.3.2 DISPOSITION, DEMOGRAPHICS, AND BASELINE DISEASE CONDITION

Patient disposition, baseline demographics, and baseline disease condition will be summarized.

14.3.3 EXPOSURE TO TREATMENT

The summary of exposure will include the final idronoxil and doxorubicin doses, and the cumulative doses of idronoxil and doxorubicin received over the course of the entire study. Summaries will also be provided of the number of idronoxil treatments missed, the number of changes in the idronoxil and doxorubicin doses, the number of patients receiving dexamethasone, and the dexamethasone dose.

14.3.4 ADVERSE EVENTS

An AE will be deemed treatment emergent (TEAE) if it starts or worsens in severity or toxicity after the beginning of treatment, whether with idronoxil or with idronoxil + doxorubicin.

Adverse events will be coded using the MedDRA Dictionary, Version 22.0 (or higher). Treatment emergent adverse events will be summarized by MedDRA Preferred Term and System Organ Classification for each dose group. Separate summaries will be provided for TEAEs with onset prior to the first dose of doxorubicin, with onset during the first cycle of idronoxil+ doxorubicin therapy, and for TEAEs with onset after the end of the first treatment cycle.

The toxicity of an AE will be assessed by the NCI-CTCAE, Version 5.0. Summaries of TEAEs will be provided by dose group and toxicity grade. Summaries of TEAEs will also be provided by dose group and Investigator-reported severity and by dose group and Investigator-reported relationship to study treatment.

A summary will be provided of the overall incidence and the incidence of component terms for the Standardized MedDRA Queries (SMQs) for Cardiac Failure and for Cardiomyopathy.

A separate summary will be provided of Serious Adverse Events (SAEs) by dose group. Summaries will be presented for all SAEs, for treatment-emergent SAEs, for treatment-emergent SAEs that occur prior to the first dose of doxorubicin, during the first cycle of idronoxil + doxorubicin combination treatment, and after the end of the first cycle of combination treatment.

Deaths on study or within 30 days after a patient exits the study will be summarized by treatment. A listing of all deaths will be provided.

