11.2.2 TREATMENT DISCONTINUATION

Patients will be discontinued from the study treatment if any of the following occurs as noted in Section [9.5](#).

- Disease progression based on RECISTv1.1
- An inter-concurrent illness that prevents further administration of NOX66
- An adverse event that is intolerable to continue the treatment with NOX66 and doxorubicin or any DLT (Section [8.3](#)) that has not resolved to Grade 1.
- Any other reason the Investigator considered that impacts the patient's safety.

For the patients who discontinue treatment, they will continue on study for follow-up visits for tumor evaluation. All anti-cancer treatments should be recorded in the eCRF. In those patients who have evidence of disease progression during the combination of NOX66 and doxorubicin, additional tumor evaluation assessments are not needed.

If a patient is withdrawn from the study at any time, either at his/her request or at the Investigator's discretion, regardless of the reason, the Investigator will record on the relevant page of the eCRF the reason(s) for withdrawal and the day of last dosing. The eCRF (and the clinical study report) will include reasons for patient withdrawals, as well as other details relevant to the patient's withdrawal.

Any patient who appears to be noncompliant from Cycles 2 to 6 should be counselled but not withdrawn from the study. Patients who discontinue for non-safety related reasons or for noncompliance prior to the end of Cycle 1 in the Dose-Escalation Part can be replaced.

Should any patient withdraw or be withdrawn from the study prior to the completion of the Month 18 follow-up visit, every effort should be made to complete the assessments at the End of Study (Section [11.6.2.12](#)). Patients experiencing adverse events should be followed until the AE has resolved, stabilized, or is no longer deemed clinically significant, as judged by the Investigator. Appropriate supportive and/or definitive therapy will be administered as required.

Discontinuation due to treatment failure, as defined by disease progression, is to be expected since doxorubicin is not curative for sarcoma and the optimal dose and dose frequency is not known for NOX66. Alternate treatments for sarcoma may be offered to the patient.

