11.3 STUDY PROCEDURES

[figure not shown]
This study will be conducted in three parts each with screening, treatment and follow up periods as outlined in [Table 2](#). In the Dose Escalation Part, patients receive NOX66 monotherapy followed by NOX66 and doxorubicin combination therapy. In the Dose Expansion Part, patients receive NOX66 and doxorubicin combination therapy only. Patients in each part will be followed post therapy for about 14 months. An overview of phases of the study by period is shown below ([Table 2](#) and [Figure 1](#)).

Table 2 Treatment Periods

	Dose Escalation Only		Dose Escalation & Dose Expansion								
Screening	Monotherapy	Washout	Combination Treatment Cycles [#] 6 Cycles X 21 Days	Follow-Up from C1D1					Month 18 EOS (18 M from C1D1)		
				Month 6 (6 M from C1D1)	Month 9 (9 M from C1D1)	Month 12 (12 M from C1D1)	Month 15 (15 M from C1D1)				
28 days	7 days	5 days	126 days	1.8 M from C6D21	3 M from last f/u	3 M from last f/u	3 M from last f/u	3 M from last f/u			
	12 days		4.2 Months	1.8 Months	3 Months	3 Months	3 Months	3 Months			
1.3 Months			18 Months								
~ 20 Months											

C1D1 = Cycle 1 Day 1; EOS = End of Study; f/u = follow-up, M = month

[#]Each combination therapy cycle is 21 days with NOX66 administered on Days 1-7 at a fixed dose and regimen. On Day 2 doxorubicin is administered intravenously for 15 minutes at 75 mg/m². No treatment is administered on Days 8-21. During the follow-up period, neither NOX66 or doxorubicin is administered, but other approved or investigational medication for sarcoma may be administered.

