11. The additional tests for hematology and serum chemistry on Days 9 and 16 are to assess any hematological or clinical laboratory tests for DLTs and/or require a dose reduction to 60 mg/m^2 or lower (37.5 mg/m^2 or 18.75 mg/m^2 based on serum bilirubin), or a delay in initiation of another cycle of the combination. These additional hematological and clinical laboratory tests should be performed at each cycle. Visit windows are ± 2 days of the scheduled visit.
12. During combination treatment cycles, NOX66 is administered on Days 1 to 7 and doxorubicin is administered on Day 2.
13. Doxorubicin (75 mg/m^2 or reduced dose) to be given on Day 2 of each 21-day cycle.
14. For Dose-Escalation Cohorts, PK samples will be obtained at pre-dose and at 1 and 2 hours post NOX66 on Day 2 Cycle 1. PK samples for idronoxil will be obtained on Day 2 of Cycles 2, 4 and 6 at pre-dose and 4 hours post dose. Additional PK samples for idronoxil will also be obtained pre-dose on Day 7 and at 8 or 12 hours after the last dose of NOX66 on Day 7 for those on a TID or BID regimens, respectively on Cycles 1, 3, and 5. For the Dose Expansion Cohort, PK samples for idronoxil will be obtained on Day 2 of Cycles 1, 2, 4, and 6 at pre-dose and at 4 hours post NOX66 and on Cycle 1 at 6 hours post NOX66. On Cycles 1, 3, and 5 PK samples are to be collected just prior to the morning dose of NOX66 on Day 7. For doxorubicin in the Dose Escalation Cohort, PK samples will be obtained at 0.5, 4 and 6 hours after the end of infusion on Day 2 Cycle 1 and at 0.5 and 4 hours at the end of infusion on Day 2, Cycles 2, 4 and 6. For doxorubicin in the Dose Expansion Cohort, PK samples will be obtained at 0.5, 4 and 6 hours after the end of infusion on Day 2 Cycle 1 and at 0.5 and 4 hours at the end of infusion on Day 2, Cycles 2, 4 and 6 ([Table 7](#)).
15. All patients who discontinue the study early for whatever reason after the first dose of NOX66, or during treatment cycles (Cycles 1-6), will be followed up within 28 days of discontinuation and submit to assessments detailed in the column of Cycle 6 Day 21/Early Termination. Patients who discontinue the study early during the follow-up period will complete a final visit with assessments detailed in the column of End of Study/Early Termination. Patients who complete the study in full will have an End of Study visit at Month 18.
16. Adverse events to be recorded up to 30 days after the last dose of NOX66 or doxorubicin, whichever is longer.

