15.2.1.1 AE Reporting

All AEs are graded according to NCI-CTCAE v5.0. AEs are captured from the time of consent and must be reported in the eCRF.

. Some events may make the patient ineligible for enrollment. Unanticipated events should be reported to the IRB, according to its requirements. Patients will be questioned at every visit after the first dose until the last follow-up visit regarding the occurrence and nature of any TEAEs. All TEAEs will be reported, whether or not they are deemed to be related to investigational product.

A description of the event or diagnosis including dates, severity, relationship to the investigational product, action taken and outcome, and whether or not the event was also serious, must be reported on the AE eCRF for each TEAE recorded in the patient's chart.

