Pre-existing conditions or illnesses which are expected to exacerbate or worsen are not considered adverse events and will be accounted for in the patient's medical history.

All adverse events are to be followed up for 30 days post the last dose of study drug or until resolution (whichever is sooner).

Adverse events reported by the patient or observed by the Investigator will be listed individually on an adverse event form in the eCRF. The signs and symptoms, time of onset, criteria for assessing causality to study drug ([Table 5](#)) and outcome categories should be defined ([Table 6](#)). In order to classify AEs and diseases, preferred terms and system organ classes will be assigned by the Sponsor to the original terms entered on the eCRF using the Medical Dictionary for Regulatory Activities (MedDRA) (Section 13.2.1).

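### The TEAE definition has no end and the AE collection period is stated two ways, so off-drug events may enter the overall and post-Cycle 1 dose-group tables

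*Combined protocol and SAP*

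**What the plan says.** **Definition and tables (Section 14.3.4).** The definition has a start only: "An AE will be deemed treatment emergent (TEAE) if it starts or worsens in severity or toxicity after the beginning of treatment". On its use: "Treatment emergent adverse events will be summarized by MedDRA Preferred Term and System Organ Classification for each dose group". Separate summaries are planned by time of onset: before doxorubicin, during Cycle 1, and a last group "for TEAEs with onset after the end of the first treatment cycle". That last group has no end either. TEAEs are also tabulated by grade, severity and investigator-reported relationship, and SMQ summaries are planned for Cardiac Failure and Cardiomyopathy.

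**Short collection period.** Table 4 footnote 16 says: "Adverse events to be recorded up to 30 days after the last dose of NOX66 or doxorubicin, whichever is longer". Section 16.2.2 names only treatment-related events for reporting after 30 days.

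**Long collection period.** Section 15.2.1.1 says: "Patients will be questioned at every visit after the first dose until the last follow-up visit regarding the occurrence and nature of any TEAEs". Section 11.4.2.4 has AEs recorded for the whole study. Sections 11.6.2.10 to 11.6.2.12 schedule AE or TEAE review at Months 6, 9, 12, 15 and 18, and the follow-up part of Table 4 marks AE recording at the same visits.

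**Treatment in follow-up.** The note to Table 2 (Section 11.3) says that NOX66 and doxorubicin are no longer given but "other approved or investigational medication for sarcoma may be administered". Section 11.2.2 requires all anti-cancer treatments to be entered in the eCRF.

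**Follow-up of an open AE.** Section 16.1.1 ends it at 30 days after the last dose, or at resolution if that comes first. Section 11.2.2 says: "Patients experiencing adverse events should be followed until the AE has resolved, stabilized, or is no longer deemed clinically significant".

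**The concern.** Safety is the primary analysis and AEs are a primary endpoint (Section 11.1.1). With no end to the window, an event in Month 14 under a different sarcoma drug meets the definition in the same way as one in Cycle 2, and it is tabulated under the patient's NOX66 dose. Patients followed longer have more time to accrue such events.

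Escalation groups have 3 or 6 patients. One patient with an off-drug event moves an incidence by 1/3 = 33 or 1/6 = 17 percentage points.

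The second problem is in the data. A site that works from footnote 16 and a site that works from Section 15.2.1.1 can each be following the protocol and still return different late AEs. No analysis rule can restore events that were never collected.

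**Working it through.** **1. Reproduce the plan's timeline.** Six cycles of 21 days are 126 days. 126 / 30 = 4.2 months, and 18 − 4.2 = 13.8 months, which agrees with the stated post-therapy follow-up of about 14 months. Table 2 also sums: 4.2 + 1.8 + 4 × 3 = 18.0 months from Cycle 1 Day 1.

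**2. Place the 30-day limit for a six-cycle completer on schedule.** NOX66 is given on Days 1 to 7 and doxorubicin on Day 2, so the last NOX66 dose sets the limit. A month is taken as 30.44 days.

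| | Escalation (12-day lead-in) | Expansion |
|---|---|---|
| Last NOX66 dose | 12 + 5 × 21 + 7 = day 124 | 5 × 21 + 7 = day 112 |
| Plus 30 days | day 154 | day 142 |
| Month 18 | 12 + 18 × 30.44 ≈ day 560 | 18 × 30.44 ≈ day 548 |
| Share beyond the limit | 1 − 154/560 ≈ 72% | 1 − 142/548 ≈ 74% |

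With 30-day months the shares are 72% and 74% as well.

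**3. The post-Cycle 1 group and early stoppers, counted from Cycle 1 Day 1.** Post-Cycle 1: (548 − 142) / (548 − 21) = 406/527 ≈ 77%. Stop after 4 cycles: the limit is 3 × 21 + 7 + 30 = day 100, and 1 − 100/548 ≈ 82%. Stop after 2 cycles: the limit is 21 + 7 + 30 = day 58, and 1 − 58/548 ≈ 89%. The Month 6 visit (6 × 30.44 ≈ day 183) is already 41 days past the completer's limit.

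**4. What this could mean in patients.** The document gives no late event rate, so the rate here is an assumption. For an event unrelated to study drug at a constant rate r per patient-month, the share with at least one event by t months is 1 − exp(−r·t). Day 142 is 4.67 months.

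| Assumed r | To day 142 | To Month 18 |
|---|---|---|
| 0.01 | 4.6% | 16.5% |
| 0.02 | 8.9% | 30.2% |
| 0.05 | 20.8% | 59.3% |
| 0.10 | 37.3% | 83.5% |

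These figures assume full follow-up. Death and dropout lower the last column. If footnote 16 governs all AE recording, the excess is close to zero.

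**5. Does footnote 16 settle the matter?** In Table 4 it is attached to the AE rows of the treatment-cycle grids. The AE row of the follow-up grid carries footnote 17, which concerns only the Month 15 telephone contact or chart review. So the 30-day limit is not tied to the visits where it matters, and Section 15.2.1.1 contradicts it directly.

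**The case against.** **The 30-day reading has real support.** Sections 11.6.2.10 and 11.6.2.12 refer sites to Section 16, which contains the 30-day rules, and Section 16.2.2 names only related events afterwards. A reader might infer that AEs are certainly collected to Month 18 and that the tables will be contaminated. The document does not support that: the collection period is unsettled. This part of the objection stands, and the effect is possible rather than certain.

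**Progression is mostly excluded.** A reader might infer that progression events will fill the TEAE tables. Section 16.1.1 does not count the studied disease as an AE unless its course is worse than anticipated, and Section 16.1.2 keeps documented progression out of SAE reporting. Symptoms of progression could still be recorded, but progression itself largely could not.

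**Section 14.3.4 has partial safeguards.** Late events do not belong in the pre-doxorubicin or Cycle 1 groups, and the relationship table helps the reader. That table is not a full safeguard, because Section 14.3.1 counts a missing relationship as definitely related.

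**The percentages are time, not events.** They are maxima for a patient followed to Month 18. Section 6.1 puts median survival at about 12 months historically and 18 to 19 months in recent trials, so many patients will contribute less.

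**A hard cut at 30 days has a cost.** Post-treatment ECGs are planned, and echocardiograms where doxorubicin was stopped for cardiac toxicity. Listing only later related events would hide late cardiac events from the planned SMQ summaries. This stands and shapes the fix.

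**Details are deferred to an SAP (Section 14.3.12).** An SAP could close the window, but it cannot make sites collect the same data.

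**Conclusion.** The point holds in limited form. The TEAE window has no end, and AE collection is stated both as 30 days after the last dose and as through Month 18, with other sarcoma therapy allowed in between. The exposed outputs are the overall TEAE table and the post-Cycle 1 table, where events from later therapy may be counted against NOX66 dose groups.

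The size is an upper bound on calendar time: about 72% (escalation) or 74% (expansion) for a patient who completes six cycles without delay and is followed to Month 18. It would be wrong to read this as 72% of TEAEs being off-drug, since the number of such events cannot be derived from the document.

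Nor is dose finding compromised. DLTs and the MTD rest on Cycle 1 (Sections 8.3.1 to 8.3.3), and the pre-doxorubicin and Cycle 1 tables are not affected.

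The conflict over how long an open AE is followed is real but separate. It does not change an event's onset, so it does not bear on TEAE classification. The change should be made, but it does not threaten the trial's main decision.

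**What to change.** - **Section 14.3.4:** define the on-treatment TEAE window as first dose of study drug to 30 days after the last dose of NOX66 or doxorubicin, which is footnote 16's own figure. Flag events that start after new anticancer therapy; Section 11.2.2 already has those treatments recorded.
- **Later-onset AEs:** present them in a separate post-treatment summary by dose group, not only in a listing of related events.
- **Cardiac Failure and Cardiomyopathy SMQs:** keep these summaries over the whole study, split into on-treatment and post-treatment.
- **Collection:** reconcile Sections 11.4.2.4, 11.6.2.10 to 11.6.2.12, 15.2.1.1 and 16.2.2, the follow-up part of Table 4 and footnote 16 to one rule, and attach the right footnote to the follow-up AE row.
- **Separately:** reconcile the AE follow-up duration in Section 16.1.1 with Section 11.2.2.

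The cost is wording in the protocol and SAP, derived flags for the window and for new therapy, and one extra table. TEAE counts in the main tables will be lower, and the post-treatment summary shows where the remaining events went.

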	
replaced in the Monotherapy period, in Cycle 1 or 2, the number of patients will be higher than 34.
 
Analysis sets:
 
There will be two analysis sets
 
• Safety Set: All patients treated with at least one dose of idronoxil will be included in the Safety Set (SS). All analyses of safety, toxicity, and PK will be performed for this set.• Full Analysis Set (FAS): All patients who completed at least one cycle of combination therapy (at any NOX66 dose). 
Analyses of efficacy, tolerability, and biomarkers will be performed for the FAS. Separate summaries may be provided for patients participating in the Dose Escalation and Dose Expansion parts.
 
Safety (Primary analysis):
 
The safety profile will be based on Serious Adverse Events (SAEs), Treatment Emergent Adverse Events (TEAEs), standard clinical laboratory parameters (clinical chemistry, hematology, urinalysis), vital signs measurements, ECG parameters, and physical examination findings.
 
Adverse events (AE) will be coded using the Medical Dictionary for Regulatory Activities and summarized by dose when NOX66 is given alone or in combination with doxorubicin. The number and percentage of patients reporting TEAEs will be calculated overall, by system organ class, and by preferred term for each dose level. Adverse events will also be graded for severity according to the National Cancer Institute Common Terminology Criteria for Adverse Events, Version 5.0.
 
Serious Adverse Events (SAEs) will be summarized separately.
 
Cardiac AEs (including clinically significant abnormalities in ECG rhythm and waveform morphology reported as TEAEs) and changes in echocardiographic parameters will be summarized.
 
Descriptive statistics will be provided for demographics, baseline characteristics, and exposure to treatment by cohort.
 
Univariate summary statistics will be provided by dose group at each visit for quantitative laboratory parameters and vital signs and for the change from baseline in these parameters. For laboratory values and vital signs with defined CTC grades, shift tables will be provided for CTC grades from baseline to end of study and from baseline to worst value on study.
 
Univariate summary statistics will be presented for ECG parameters for the value at each measurement time point and the change from baseline to each measurement time point. A similar analysis will be provided for the worst value of each ECG parameter on study.
 
Findings from physical examinations and ECOG performance status will be summarized by dose of NOX66 given alone or in combination with doxorubicin.
 
Pharmacokinetics (Secondary analysis):
 
Individual blood concentration-time data and blood PK parameters will be summarized using descriptive statistics by dose and sampling time for idronoxil and metabolites. Separate summaries will be provided for PK

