7 STUDY OBJECTIVES

7.1 PRIMARY OBJECTIVES

- To estimate the maximum tolerated dose (MTD) of NOX66 in combination with doxorubicin
- To characterize the safety and tolerability of NOX66 alone and in combination with doxorubicin.

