8.1.1 DOSE-ESCALATION

For all dose escalation cohorts, there will be 7 days of monotherapy treatment with NOX66 followed by a 5- day washout period prior to the start of combination cycles of NOX66 and doxorubicin. The purpose of the monotherapy treatment is to evaluate the safety and tolerability of NOX66 when administered alone and as well as single and multiple dose PK of idronoxil.

The dose-escalation part of the study will include three planned Treatment Groups (800, 1200, 1800 mg daily) of 3 patients each. The first 3 patients will be entered at Dose Level 1 and will receive daily doses of NOX66 for 7 days. All of these doses, except for the 1800 mg have been evaluated in 2 previous clinical trials and have been relatively well tolerated as monotherapy for 14 days and in combination with carboplatin for 42 days.

After a rest period of 5 days and if no significant toxicities (DLT equivalent toxicity) have occurred, patients will enter the combination therapy part of the study which will consist of up to 6 x 21-day treatment cycles. Each cycle will consist of 7 days of NOX66 (at the assigned dose), doxorubicin (75 mg/m²) on Day 2 of the 21-day cycle (administered at approximately 1 hour after rectal application of NOX66) and a rest period of 2 weeks.

For the 800 mg and 1200 mg dose levels NOX66 will be administered twice-daily (BID) with a 400 mg or 600 mg suppository, respectively, and the 1800 mg dose level will entail administration of a 600 mg suppository three times daily (TID). In all cohorts, doxorubicin will be given initially at 75 mg/m² as an intravenous infusion over 15 minutes (or as per standard of care). This dose may be reduced to 60 mg/m², at the Investigator's discretion for unacceptable Grade ≥ 2 toxicity. A dose reduction of 50% is recommended if serum bilirubin is 1.2 -3.0 mg/dL prior to a cycle. If serum bilirubin is 3.1-5.0 mg/dL prior to a cycle, a 75% dose reduction of doxorubicin is recommended.

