8.1.2 COHORT EXPANSION

After the dose escalation part is completed, 16 patients will be enrolled into a Dose Expansion Cohort at the MTD of the combination. All patients will enter directly into 21-day combination cycles and will be given NOX66 therapy for 7 days and doxorubicin will be administered on Day 2. This will be followed by a 2-week rest period. Treatments will continue up to 6 cycles.

For both the Dose Escalation and Cohort Expansion groups, treatment will be terminated upon disease progression, unacceptable toxicity or a maximum of 6 cycles. In patients who develop Grade 3 or 4 toxicity determined to be related to NOX66, the Investigator may reduce the dose or frequency of dosing by one level so that the patients can remain in the study. Furthermore, all patients will be actively followed up for about 14 months after completion of Cycle 6 (including scheduled visits every 3 months) followed by telephone follow-up/chart review, for PFS and OS, at 15 and 18 months from the start of Cycle 1.

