14.2 ANALYSIS SETS

There will be two analysis sets

- Safety Set: All patients treated with at least one dose of idronoxil will be included in the Safety Set (SS). All analyses of safety, toxicity, and PK will be performed for this set.
- Full Analysis Set: All patients who complete at least one cycle of idronoxil + doxorubicin combination therapy will be included in the Full Analysis Set (FAS). Analyses of efficacy, tolerability, and biomarkers will be performed for this set.

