14.3 STATISTICAL METHODOLOGY

14.3.1 GENERAL STATISTICS METHODS

All data will be summarized by idronoxil dose group. For safety analyses, a summary group consisting of all dose groups combined may also be presented.

For all measurements, the baseline value will be the last measurement taken before the first dose of study drug, whether idronoxil or of idronoxil + doxorubicin depending on the cohort.

Standard summary statistics will be presented for all measurements. For continuous variables, the standard summary statistics will be the number of observations (n), mean, standard deviation, median, minimum and maximum. For categorical variables, the standard summary statistics will be the number and percentage of observations in each category. Categories that are specified on the eCRF which contain no observations will be presented in the data summaries with a value of 0.

An AE with a completely missing start date will be assumed to start one minute after the date-time of the first idronoxil dose. If the severity of a reported AE is missing, it will be assumed that the event is severe; similarly, if the relationship of a reported AE to study treatment is missing, it will be assumed that the event is definitely related to treatment. No other missing data will be imputed. Incomplete start dates for Adverse Events and Concomitant Medications and incomplete end dates for AEs will have missing parts imputed by a conservative procedure which will be specified in the Statistical Analysis Plan (SAP).

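### The pre-doxorubicin adverse event tables need not be split by study part, so the MTD column can mix 13-day and 1-day windows on NOX66 alone in one percentage

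*Combined protocol and SAP*

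**What the plan says.** One of the two primary objectives (Section 7.1) is "To characterize the safety and tolerability of NOX66 alone and in combination with doxorubicin". Three provisions fix how the NOX66-alone part is reported:

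- **Window.** Section 14.3.4: "Separate summaries will be provided for TEAEs with onset prior to the first dose of doxorubicin". The other two windows are the first combination cycle and the time after it. SAEs are cut the same way.
- **Grouping and statistic.** Section 14.3.1: "All data will be summarized by idronoxil dose group". The synopsis adds: "The number and percentage of patients reporting TEAEs will be calculated overall", and then by system organ class and preferred term for each dose level. Nothing adjusts for time at risk.
- **Population.** The Safety Set in 14.2 takes in everyone who received any idronoxil, in either part.

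The two parts reach doxorubicin by different routes. For escalation cohorts, Section 8.1.1 states that "there will be 7 days of monotherapy treatment with NOX66 followed by a 5- day washout period"; doxorubicin follows on Day 2 of Cycle 1. For expansion, Section 8.1.2 states: "All patients will enter directly into 21-day combination cycles and will be given NOX66 therapy for 7 days", again with doxorubicin on Day 2. Section 6.2 confirms that expansion patients have one day of NOX66 before doxorubicin.

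The only provision for separating the parts is in the synopsis, under analysis sets: "Separate summaries may be provided for patients participating in the Dose Escalation and Dose Expansion parts". Section 14 does not repeat it.

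**The concern.** All expansion patients are treated at the MTD, so they fall into the same idronoxil dose group as the escalation patients at that dose. A patient observed for one day has had little chance to report a NOX66-alone event, yet counts in the denominator as fully as one observed for 13. Only the MTD column is affected, and that is the dose taken into expansion.

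The pre-doxorubicin table is a main planned readout of NOX66-alone toxicity. Under 8.3.3, toxicity in the monotherapy period is recorded as DLT-equivalent and is not counted as a DLT. Under 8.3.6, a patient who does not tolerate monotherapy may be replaced.

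There is also a smaller defect. Cycle 1 Day 1 lies before the first doxorubicin dose and inside the first combination cycle, so an event with onset that day fits two of the three windows.

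**Working it through.** **Planned numbers.** The synopsis gives about 28 patients as the minimum and about 34 as the maximum. These reproduce as 3 + 3 + 6 + 16 = 28 and 18 + 16 = 34. The planned MTD column is therefore 6 escalation patients plus 16 expansion patients, 22 in all, and 16/22 = 73% of them come from expansion.

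**Time before doxorubicin.** Escalation: 7 + 5 + 1 = 13 calendar days, of which 7 + 1 = 8 are dosing days. Expansion: 1 day. Patient-days: 6 × 13 = 78 and 16 × 1 = 16, so expansion supplies 73% of the patients but 16 of 94 patient-days (17%).

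**Dilution factor.** Let p be the proportion of escalation patients with a pre-doxorubicin TEAE, and s the ratio of the expansion proportion to p. The pooled proportion is (6p + 16sp)/22, so the factor is 22/(6 + 16s). The documents give no NOX66-alone event rate or onset profile for this regimen, so s is an assumption and a range is needed.

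| Assumption about s | Factor |
|---|---|
| No Day 1 event in expansion (s = 0) | 22/6 = 3.67 |
| Constant event rate, calendar days (s = 1/13) | 286/94 = 3.04 |
| Constant event rate, dosing days (s = 1/8) | 176/64 = 2.75 |
| A quarter of affected patients have onset on Day 1 | 22/10 = 2.20 |
| Half have onset on Day 1 | 22/14 = 1.57 |
| All have onset on Day 1 | 22/22 = 1.00 |

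**Patient proportions.** With a constant daily risk over d days, the one-day proportion is 1 − (1 − p)^(1/d):

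| p | Pooled, d = 13 (factor) | Pooled, d = 8 (factor) |
|---|---|---|
| 10% | 3.3% (3.02) | 3.7% (2.72) |
| 50% | 17.4% (2.87) | 19.7% (2.54) |
| 90% | 36.4% (2.48) | 42.7% (2.11) |

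**Replacements.** Section 8.3.6 allows up to 3 replacements per dose level in the monotherapy period, and replaced patients stay in the Safety Set. With 9 + 16 patients the ceiling is 25/9 = 2.78; the constant-rate factors are 2.44 (calendar days) and 2.27 (dosing days).

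**Illustration.** If 2 of 6 escalation patients are affected and no expansion patient is, the table shows 2/22 = 9.1% where the lead-in gives 2/6 = 33.3%. If nobody is affected, the one-sided 95% upper bound, 1 − 0.05^(1/n), is 39% for n = 6 and 13% for n = 22. The tighter bound comes from patients observed for one day.

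**The case against.** The strongest reply is that pooling is inferred. Neither 14.3.1 nor 14.3.4 says that the two parts share a column. The synopsis permits a split and gives exposure by cohort, which would show the imbalance. Section 14.3.12 leaves presentation to a separate SAP, to be approved before the expansion cohort opens, and that SAP is not among the documents. This stands to the extent that pooling is the default reading and not a stated rule. It does not remove the point. The synopsis uses dose, not cohort, for adverse events. Section 14.3.5 limits its Day 7 cytokine summary to escalation patients, while 14.3.4 has no such limit. A permitted split does not secure a table that serves a primary objective.

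Two stronger inferences are tempting, and the documents do not support them.

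- **That NOX66-alone toxicity at the MTD will be diluted almost fourfold.** That is the ceiling, and it needs zero Day 1 events among 16 patients. Five of the 13 days are also off drug.
- **That a dose trend would be reversed, or the MTD chosen wrongly.** Suppose 3/6 affected at 1800 mg and 1/3 at a lower dose. Pooling would bring the 50% down to about 17 to 20% under a constant rate, below 33%. But those counts are invented, and the exact 95% interval for 3/6 is 12 to 88%, so no trend could be read even without pooling. MTD selection uses Cycle 1 DLTs reviewed cohort by cohort (8.3, 15.2.1), and expansion starts only after escalation is complete.

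**Conclusion.** The concern holds as a gap in the reporting rules. Followed as written, 14.3.4 with 14.3.1 and 14.2 yields an MTD percentage in which roughly three quarters of the denominator had one day at risk and the rest had 13. The displayed NOX66-alone incidence can be too low by a factor of up to 3.7 (2.8 with three replacements), about 2 to 3 if the event rate is constant, and less if onset is early. These figures assume the planned 6 + 16 patients (9 + 16 with replacements) and pooling by dose group. The consequence is confined to the reported NOX66-alone safety profile. The Cycle 1 Day 1 overlap is real whatever the dilution, but concerns a single day.

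**What to change.** In 14.3.4:

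1. Make the split by study part mandatory for the pre-doxorubicin TEAE and SAE tables.
2. Take the NOX66-alone incidence at each dose from Dose Escalation patients who started monotherapy, including those later replaced.
3. Show the expansion patients' single pre-doxorubicin day in its own column, labelled with its length.
4. Define the second period as starting at the first doxorubicin dose, so that a Cycle 1 Day 1 event is counted once, as pre-doxorubicin. Starting that period at Cycle 1 Day 1 would also remove the overlap, but it would move NOX66-alone events into the combination period.

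The cost is wording and table shells, with no new data, and it can be settled in the SAP that 14.3.12 requires before the expansion cohort opens. The downside is a NOX66-alone denominator at the MTD of about 6 instead of 22, with a correspondingly wider interval.
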